The study nurse will use software already developed for previous Durham HSR&D Center of Innovation (COIN) studies including DISPO ED, to guide content delivery during calls, including scripts and questions for patients. This software adheres to current VA information security standards, and will be linked with a secure SQL Server database, following procedures developed by COIN IT staff and used successfully by numerous COIN investigators. Patients are offered printed and mailed information about the topics discussed if they desire, including how to reach the study nurse for additional questions or issues. Each call will end with open-ended questions, allowing Veterans to describe additional needs that were not addressed. In order to understand staff time needed for the full intervention, we will carefully track interventionist time spent on calls (including attempted and incomplete calls), reviewing medical records, and documenting and making referrals.

D.5. Arm 2: Video-Enhanced Care Management Intervention. Patients randomized to Arm 2: Video-Enhanced Care Management Intervention will receive the same number of contacts delivered on the same schedule and focused on the same key components as the telephone-based program. The primary difference in the video-enhanced intervention is that the nurse will communicate with the patient and Care Partner using video visits in secure Virtual Meeting Rooms, facilitated through the Pexip Infinity applications (version 12.2) on iPads. We will use tablets (instead of desktop or laptop computers) so that participants can move them around easily if needed to facilitate observation of the Veteran or some aspect of their home environment; iPad is a tablet approved for use with the Pexip Infinity application (version 12.2). Table 2 summarizes the supplemental strategies that may be used in the video-enhanced intervention. Any scheduled video visits not able to be completed due to a technology problem will be conducted over the telephone. The nature and type of any technology limitations will be closely tracked.

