D.5.a. Installing software for video calls. Participants who have their own iPad will be able to utilize it for the study. Patients who do not have access to an iPad will be loaned one for use during the study. All participants will be provided with detailed instructions for installing the Pexip Infinity application (version 12.2) application or have the application pre-installed on their device) and will have access to IT support over the telephone or in-person at the Durham VA with a study staff member and the facility telehealth coordinator if needed.

Consistent with current clinical policy for video visits, study staff will collect participant emails addresses to send an encrypted email to facility telehealth team for scheduling purposes. Emails addresses will not be stored in VA research databases. Research staff will not directly send or receive any emails to patients. All patients will participate in a test call with facility telehealth staff before scheduling their first study nurse call. We allot 2 weeks from the time of enrollment for the Pexip installation and completion of a test call. If the patient cannot complete the Pexip Infinity application (version 12.2) installation within this 2-week time frame (for any reason), the intervention will continue using telephone calls only. All patients in the Video-Enhanced Care Management Program (Arm 2) will be provided with an iPad cover with built-in stand and keyboard to make logging into Pexip easier and quality of video interaction better.

D.5.b. Technology solution for video calls. We have selected the Pexip Infinity application (version 12.2) for the video calls for several key reasons: 1) this technology meets all VA security standards and is currently in use

for in-home video telehealth encounters throughout VHA (FaceTime, Skype, etc. are not approved for use by VA clinicians); 2) facility telehealth coordinators can provide ongoing IT support (see Telehealth Coordinator letter of support); and 3) use of a tablet (iPad) enables mobility of the device to expand the applications of the video link to viewing aspects of the users home environment.

D.6. Measures and Data Sources

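### The staff-time log is meant to cover the full intervention but records interventionist time only, so video-arm set-up and support time goes uncounted

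*Combined protocol and SAP*

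**What the plan says.** Section D.4.b, on the content and delivery of nurse calls, sets up the log: "In order to understand staff time needed for the full intervention, we will carefully track interventionist time spent on calls". The sentence then widens the log a little, "including attempted and incomplete calls), reviewing medical records, and documenting and making referrals". It names no other activity and no other staff role.

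Section D.5.a, under Arm 2, describes what must happen before and around a video visit:

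- **Test call:** "All patients will participate in a test call with facility telehealth staff before scheduling their first study nurse call".
- **Installation and IT help:** participants "will have access to IT support over the telephone or in-person at the Durham VA with a study staff member", and the facility telehealth coordinator joins if needed.
- **Scheduling:** "study staff will collect participant emails addresses to send an encrypted email to facility telehealth team for scheduling purposes".
- **Devices:** Veterans without an iPad are loaned one, the application may be pre-installed, and every Arm 2 patient receives a cover with stand and keyboard.

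Section D.5.b gives, as one reason for choosing the platform, that "facility telehealth coordinators can provide ongoing IT support". Section D.5 says that the kinds of technology limitation met will be tracked. It does not mention the staff time they take.

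Sections D.4 and D.4.a also have the nurse accompany patients to a PCP visit if one is scheduled during the study. Section D.7 does not mention staff time at all.

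**The concern.** The purpose is broader than the rule. The purpose is the staff time that the whole intervention needs, and the rule counts one role. For the telephone arm the two are close. For the video arm, a block of necessary work is done by people whose time is not recorded.

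The plan does not treat that work as trivial. It allots 2 weeks to installation and the test call (D.5.a) and starts nurse calls 2 weeks after randomization for that reason (D.4.a). It also stratifies randomization on technology experience (D.3.h). In its own survey (Table 1), 40% of Veterans and 26.3% of caregivers aged 65 or over had used videoconferencing.

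At stake is planning information for the larger trial. Section B.3.c asks for scalable care models, and D.8 says the pilot addresses whether video is feasible and adds benefit over telephone. Someone who budgets staff from this log would lack the telehealth and support component. Those minutes are hard to reconstruct if they are not written down when they occur.

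**Working it through.** The plan states no staff-time figure, so there is none to reproduce. The check has two parts: set the work against the log, then count what can be counted.

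**1. Work against log**

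| Work | Section | Who does it | Arm | Listed in log? |
|---|---|---|---|---|
| Nurse calls, including attempted and incomplete | D.4.b | Nurse | Both | Yes |
| Record review, documentation, referrals | D.4.b | Nurse | Both | Yes |
| PCP visit | D.4, D.4.a | Nurse | Both | No |
| Test call | D.5.a | Facility telehealth staff | Video | No |
| Scheduling email | D.5.a | Study staff | Video | No |
| Installation and IT help | D.5.a, D.5.b | Study staff, telehealth coordinator | Video | No |
| Device preparation | D.5.a | Not named | Video | No |

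Section D.5.a speaks of all patients and all participants. It sits under Arm 2 and concerns video installation, and D.4 says that Arm 1 contacts other than the PCP visit are by telephone. Reading this work as specific to video is therefore reasonable.

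**2. Counts from the plan**

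- Veterans per arm: 40 dyads at 1:1 (D.1) gives 40 / 2 = 20.
- Scheduled nurse calls per arm: 4 each (D.4.a) gives 20 × 4 = 80.
- Planned test calls: 20 × 1 = 20 in the video arm, 0 in the telephone arm.
- Planned scheduled contacts: 80 + 20 = 100 for video against 80 for telephone. The log would show 80 and 80, so 20 / 100 = 20% of the video-arm contacts fall outside it. This is a share of contacts, not of time.

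**3. Hours, under an assumption**

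Let *m* be minutes of set-up and support per video-arm Veteran. The documents give no value, and 10 to 90 is assumed. Unlogged hours = 20 × *m* / 60.

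- *m* = 10: 200 / 60 = 3.3 hours
- *m* = 30: 600 / 60 = 10 hours
- *m* = 60: 1,200 / 60 = 20 hours
- *m* = 90: 1,800 / 60 = 30 hours

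Let *c* be minutes per nurse call, also assumed, at 20 to 60. The unlogged share of call plus set-up time is *m* / (*m* + 4*c*).

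- Smallest: 10 / (10 + 240) = 4%
- Middle (*m* = 30, *c* = 40): 30 / (30 + 160) = 15.8%
- Largest: 90 / (90 + 80) = 52.9%

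The width of this range shows that the documents do not fix the size. The share of all staff time would be smaller, because record review and documentation would enter the denominator.

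**4. Direction**

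Setting PCP-visit time aside, the true video-minus-telephone difference per Veteran is the logged difference plus *m*. With *m* = 30:

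- equal nurse time per call: logged 0, true +30 minutes;
- video calls 5 minutes shorter: logged 4 × (−5) = −20, true +10;
- video calls 10 minutes shorter: logged 4 × (−10) = −40, true −10.

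The logged difference is too low in every case. Whether its sign changes depends on minutes that the plan does not give.

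**The case against.** The best reply is that the sentence belongs to a section on nurse calls. On that reading it means the nurse's whole workload beyond completed calls, so purpose and log agree. The reading is possible, but it does not dispose of the point. The video intervention cannot be delivered without a set-up stage to which the plan itself assigns 2 weeks, so a figure for the full intervention that omits that stage is incomplete.

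A second reply is that technology burden is partly recorded elsewhere. Nurse time on attempted and incomplete calls is logged. Technology limitations are tracked, staff feedback is sought, and the usability scale's technical-support item is singled out in D.7.b. All of that stands, but none of it gives the minutes spent by telehealth or study staff. The evaluation tables in the Appendix are not in the published text, so time capture there cannot be ruled out.

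Four stronger readings are tempting, and the documents do not support them:

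- **Video will look cheaper than it is, or an arm comparison is biased.** No costing and no by-arm comparison of staff time is planned in D.7 or D.8. The statement in D.8 about rapid implementation is conditional on effectiveness and rests on the application already being approved and in clinical use. It is not a staffing claim.
- **The log is complete for telephone.** It is not, because nurse time at PCP visits is unlisted in both arms.
- **Twenty unlogged test calls is a minimum.** It is the planned number. Veterans who cannot install the application within 2 weeks continue by telephone and may never complete a test call, although the failed attempts also take time.
- **The statement that the video arm "will receive the same number of contacts delivered on the same schedule" is contradicted by the test call.** It naturally means nurse contacts and needs no edit.

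**Conclusion.** The point holds as a gap in descriptive data. The log's stated purpose is the full intervention. Its rule covers one role, and set-up and support work that the plan assigns mainly to others for the video arm is not captured. Video-arm staff time is therefore understated relative to telephone. PCP-visit time is a second gap in the same log, common to both arms.

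The plan fixes only the counts, 20 planned test calls beside 80 scheduled nurse calls per arm. The figure of about 3 to 30 hours rests wholly on the assumed 10 to 90 minutes per video-arm Veteran. The direction rests on reading D.5.a as applying to Arm 2 only.

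No planned outcome, sample size or decision rule depends on staff time, and the pilot does no statistical testing. This is a cheap improvement and not a threat to the pilot's conclusions.

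**What to change.** In D.4.b, replace interventionist time with staff time by role and arm. To the activities already listed, add scheduling, test calls (including failed attempts), installation help, telephone and in-person IT support, device preparation, and nurse time at PCP visits.

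In D.7.a, add a descriptive summary of time per Veteran by arm with two figures: nurse delivery time, and total time including set-up and support. No test is needed.

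The cost is a few fields in the study tracking database and a small logging burden. Section D.10 limits database access to individuals on the IRB staff listing, and nothing shows that facility telehealth staff are on it. They would need a simple way to report minutes, such as a short form passed to study staff. The total-time figure will also be less favourable to video than nurse time alone.

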D.6.a. System Usability Scale. We will use the simplified language version of the System Usability Scale (SUS; see Appendix) to measure usability of video visits via iPad. The SUS is a widely-used, simple but reliable method to evaluate the usability of new technologies.³⁰ The SUS is well-validated and consists of 10 Likert-scaled items with scores ranging from 0 to 100.³¹

D.6.b. Participant and study staff feedback. Patients and Care Partners will participate in semi-structured interviews regarding perceived benefits and challenges of the care management program. Interviewer scripts will include open-ended questions about barriers and facilitators of success in the program, including technology-related, and as well as more specific questions to elicit stakeholder perspectives on intervention content, and recommendations for improvement (see Evaluation Table; Appendix). We will also seek feedback from primary care providers and study staff.

D.6.c. Measures of intervention effectiveness. In preparation for a future RCT, we will collect outcome measures we anticipate using to test intervention effectiveness. Patient reported outcomes will be examined at baseline and the 14-week follow-up call (immediately following completion of the 12-week intervention period that begins at week 2; Figure 3). Consistent with our conceptual framework, the balance of workload demands and capacity directly affect utilization and outcomes; thus we plan to focus on hospitalizations, ED visits, and patient-reported outcomes recommended for use in patients with MCC,¹⁶ that may be responsive to the intervention.

Hospitalizations and ED visits. To calculate this outcome, we add the total number of days a patient is in the emergency department (ED), or hospital. In order to avoid double-counting events, we only count ED visits as a discrete day if the ED visit did not lead to hospital admission. We include observation stays as hospital days. Data from the outpatient and inpatient files from the CDW will be used to generate counts of days associated with emergency care (treat and release), observation stays, and inpatient care, over the 14 week observation period. ED visits will be identified through the outpatient files according to clinic stop codes (130, 131, 102130 and 102131).³² Inpatient encounters will include total days in the hospital (DISDAY minus ADMITDAY).

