D.7.b. Aim 2: Assess the *usability* and *perceived value* of video-enhanced care management, compared to telephone-based, among older Veterans with medical complexity and CI. We will administer the SUS at the 14-week outcome call to participants randomized to Arm 2 (video-enhanced.), care partners, and clinical staff. If any participants choose to withdraw from this Arm, we will administer this measure prior to withdrawal. We will examine overall sample mean, median, and distributions of scores according to established thresholds (e.g. >70 = excellent usability among those aged ≥65 years). Additionally, we will look at responses to individual items to see if certain items are more frequently endorsed (e.g. technical support item) to make refinements prior to a larger RCT. We will calculate means (or medians, as appropriate) and distributions of hospitalizations, ED visits, and patient-reported outcomes (PROMIS 29, PASE, MOS Social Support, PHQ-9, GAD-7) across time points, as well as changes between baseline and 14-week follow-up, as appropriate. Because of the small sample size, we will not conduct statistical testing. However, our descriptive analyses will allow us to evaluate whether there are clinically relevant differences in mean study outcomes between the two Arms (video-enhanced vs. telephone-based). Perceived value associated with each delivery method will be explored through questionnaires and in-depth interviews with study participants and study staff.

D.7.c. Sample size considerations. This is an exploratory pilot study that is not intended to test efficacy. While the sample size chosen must reflect the pragmatics of recruitment during a short enrollment period, we will have adequate sample size to provide meaningful confidence intervals for our estimates of feasibility, and comparisons between video and telephone delivery methods, and will have sufficient diversity of input on the intervention to plan refinements, if needed, prior to testing it in a larger RCT.

D.8. Dissemination and Implementation Plan

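### An inpatient admission that starts and ends on one date adds 0 to the ED/hospital day score (below 1 if times are used), while an ED treat-and-release visit adds 1

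*Combined protocol and SAP*

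**What the plan says.** The combined protocol and SAP defines the utilization outcome in D.6.c, under Hospitalizations and ED visits. It is a single sum: "we add the total number of days a patient is in the emergency department (ED), or hospital". Three rules fill it in.

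- ED visits: "we only count ED visits as a discrete day if the ED visit did not lead to hospital admission". The stated purpose is to avoid counting an event twice.
- Observation stays: "We include observation stays as hospital days".
- Inpatient stays: "Inpatient encounters will include total days in the hospital (DISDAY minus ADMITDAY".

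The unit is again given as "counts of days associated with emergency care (treat and release), observation stays, and inpatient care, over the 14 week observation period". The documents do not say whether DISDAY and ADMITDAY are dates or date-times. They give no one-day minimum, no added day, and no rule for a stay that begins and ends on one date.

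On use, D.6.c introduces these measures with "In preparation for a future RCT, we will collect outcome measures we anticipate using to test intervention effectiveness". D.7.b states "Because of the small sample size, we will not conduct statistical testing", but adds that "our descriptive analyses will allow us to evaluate whether there are clinically relevant differences in mean study outcomes between the two Arms". The closing section on data analysis and statistical considerations also plans no statistical analysis.

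**The concern.** The ED rule and the inpatient rule count in different units inside one sum. A treat-and-release visit is worth a whole day however short it is. An admission is worth the difference between two dates, which has no floor. For a same-date admission that came through the ED, the ED day is removed because the visit led to admission, and the subtraction then contributes nothing. A rule meant to stop double-counting ends with the episode not being counted at all.

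In the summed score, a patient whose only acute event in the 14 weeks is a same-date admission would, with calendar dates, look identical to a patient with no ED or hospital use, and better off than a patient treated and released from the ED. That conflicts with the section's own aim of totalling days spent in the ED or hospital. The point concerns the summed score only: D.7.b names hospitalizations and ED visits but does not say whether event counts will also be reported.

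**Working it through.** **Inputs.** From D.6.c: a treat-and-release ED visit = 1; an ED visit leading to admission = not counted; an inpatient stay = DISDAY − ADMITDAY. From D.1: 40 dyads randomized 1:1, so 40/2 = 20 per arm. The plan gives no figure of its own to reproduce.

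**Step 1: calendar dates.** The rule as written, set against max(1, DISDAY − ADMITDAY):

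| Event | As written | With one-day minimum |
|---|---|---|
| ED treat-and-release | 1 | 1 |
| ED, then same-date admission | 0 + 0 = 0 | 1 |
| Direct same-date admission | 0 | 1 |
| One night | 1 | 1 |
| Two nights | 2 | 2 |
| Three nights | 3 | 3 |

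Only the same-date rows change. Adding one day to every stay would instead give 1, 2 and 4 for same-date, one-night and three-night stays, which rescores stays that are not in question.

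**Step 2: date-times.** A same-date stay from 09:00 to 21:00 scores 12/24 = 0.5. The longest possible, 00:00 to 23:59, scores 1439/1440 = 0.999. Both are below the 1 given to a treat-and-release visit, so the ordering is the same. On this reading a one-night stay can also fall below 1: 20:00 to 12:00 is 16/24 = 0.667. The statement that stays of one night or more are unaffected therefore holds for calendar dates only.

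**Step 3: does a minimum create double-counting?**

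- A separate treat-and-release visit and a same-date admission on one date score 1 + 0 = 1 as written, and 1 + 1 = 2 with a plain per-stay minimum. Counting the date once gives 1.
- A separate treat-and-release visit on the admission date of a one-night stay scores 1 + 1 = 2. Two dates were used, so 2 is correct and needs no adjustment.

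**Step 4: effect on an arm mean.** Each same-date stay scored 0 instead of 1 lowers its arm mean by 1/20 = 0.05 day. If it is scored 0.5, the shortfall is 0.5/20 = 0.025 day. The documents do not give the frequency of such stays. As an illustration, one to three of them, each scored 0, would lower an arm mean by 0.05 to 0.15 day. None gives 0, and equal numbers in two arms of 20, scored alike, cancel in the difference.

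**The case against.** The strongest reply is that nothing depends on this. There may be no same-date inpatient stay among 40 Veterans in 14 weeks, in which case the effect is exactly zero. No test, power calculation or decision rule uses the score, and D.8 says the pilot will be used to refine methods before the larger trial. All of this stands, and it is why the point is minor. It does not make the written rule right, and refining an outcome definition is part of what the pilot is for.

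A second reply is that the stated construct, total days in the hospital, already implies that a same-date stay counts as 1, with the parenthesis serving only to name the fields. That is a possible reading of the intent. But the subtraction is the only explicit formula, and a programmer who follows it gets 0. If the intent is 1, the formula contradicts it.

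A third reply is that counting nights is an ordinary convention under which a same-date stay naturally scores 0. That is fair for an inpatient measure standing alone. Here the nights are added to ED visits counted as whole days, and the ED visit is dropped once it leads to admission. The fault lies where the two rules meet.

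It can also be said that the date-time reading is unlikely, given field names ending in DAY and a unit of counted days. That is so. It is included only because the documents leave the fields undefined, and the conclusion does not depend on it.

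**Conclusion.** The concern holds, at minor severity. As written, the score places a same-date inpatient admission below an ED treat-and-release visit: 0 against 1 with calendar dates, or a fraction below 1 against 1 with date-times. The ordering holds on either reading; the value of exactly 0 rests on the fields being calendar dates. Confidence is high about the rule. No bias in the pilot's results has been shown, because the number of affected stays is unknown.

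**What to change.** In D.6.c, state that DISDAY and ADMITDAY are taken as calendar dates and that each inpatient stay counts as max(1, DISDAY minus ADMITDAY). Add that a date shared by a same-date stay and a separate treat-and-release ED visit is counted once; the same sentence can cover two same-date stays on one date.

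As a wording clarification only, state that the same day count applies to observation stays and that an ED visit leading to observation is not counted separately. At present the subtraction is tied to inpatient encounters, and observation stays have no formula.

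The cost is two sentences for the correction and a few lines of code. It uses the same CDW fields and needs no new data.

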Encourage physical activity.	Strong emphasis on physical activity promotion and referrals to exercise programs, c/w evidence-based benefits to physical and cognitive health	Assess physical abilities to tailor program referrals
Reduce and manage cardiovascular disease risk factors (including hypertension, diabetes, and smoking).	Individualized education for chronic disease management ; smoking cessation counseling and referral to programs to support cessation	Direct observation of patient or Care Partner checking BP, measuring blood glucose, administering insulin
Review medications that might influence cognitive health	Patient education about potentially risky medications; note in CPRS to provider when potentially inappropriate medications (PIMs, according to Beers’ criteria) are identified	Visual inspection of over the counter medications and those prescribed by outside providers as possible PIMs

D.4.a. Structure and timing of nurse contacts. Scheduled calls with the study nurse will begin 2 weeks after randomization (to reflect the time needed for the Pexip test call, Section D.5.a), and occur every 4 weeks thereafter. Beyond having a more sustained intervention period, we anticipate that more frequent contacts may be beneficial; however, in this feasibility pilot we will limit the intervention to a total of 4 scheduled calls. We will explore the potential benefits of more frequent calls in the qualitative interviews post-study completion (Section D.6.b). The Care Partner will be encouraged to participate in all calls. Also as noted in Table 2, the nurse will make additional telephone calls to patients as needed for acute events (e.g. ED visits), and will accompany the patient to a PCP visit, for those patients who have one scheduled during the intervention period.

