D.4.b. Content and delivery of nurse calls. Following procedures in use in HI-FIVES, intervention content will include both core and tailored content, selected according to participants' individual needs.²² Core topics delivered to all participants will include medication management (medication reconciliation, adherence counseling and aids if needed, and physical activity promotion (education about recommended physical activity levels and walking, personal goal-setting and program referrals (e.g. Silver Sneakers, MOVE, Gerofit). In addition, the nurse will conduct a medication review and provide a report to PCPs when potentially inappropriate medications are identified. The medication review will utilize explicit criteria (Beer's) updated by the American Geriatrics Society in 2015 focusing on medications that worsen cognition.²⁹ We focus on medications and physical activity given the evidence of both physical and cognitive benefits of improving care in these domains. The study nurse will select the topic for the 3rd call, based on needs and preferences expressed by the participant and Care Partner Consistent with our conceptual framework (Section B.5) and guiding principles for the intervention content (Table 2), other potential topics include smoking cessation, blood pressure management, diabetes care, informal care support programs, sleep patterns, and falls prevention.

Following each telephone or video visit, the study nurse will enter a note in CPRS documenting the information reviewed and referrals made. All notes will be copied to the patients' PCP and PACT Nurse. Following procedures in use in DISPO ED, the study nurse will enter unsigned orders, if needed, for the PCP to review and accept (sign). Examples include orders for exercise program referrals. This approach has been used successfully with very high uptake of recommendations (93%) in a previous VA study.²⁹

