Other Measures. We will collect information on patient socio-demographics, chronic medical conditions, self-rated health, health literacy, and sleep questions. We will review patient medical records to determine actions taken by the PCP as a result of the TICS-m score progress note (e.g. Geriatrics, Neurology referrals, Neuropsychology testing, scheduling a follow-up visit, etc.) and new diagnoses of CI or dementia.

D.7. Analyses

D.7.a. Aim 1: Examine the *feasibility* and *acceptability* of a 12-week care management program for medically complex Veterans with CI, delivered via telephone or through video visits. Feasibility will be examined by calculating overall rates of eligibility and enrollment, as well as rates of attrition, adherence to nurse calls or video visits, and interview completion. Clinical and personal characteristics associated with enrollment and study completion will be explored as well via contingency tables and regression analyses. Acceptability will be assessed using in-depth interviews with study participants (Veterans and Care Partners), primary care providers, and study staff (Section D.6.b.). We will conduct a formative evaluation of the intervention in order to elicit information about ways to enhance acceptability and effectiveness of the intervention in anticipation of testing it in a larger study.³⁸ Collecting qualitative data from relevant stakeholders including study participants, PCPs and study staff, will provide additional rich context for interpreting other quantitative study results.³⁹ Tasks and methods for each evaluation stage are described in the Appendix.

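### Could the feasibility rates hide Arm 2 Veterans who are moved to telephone because the video application was never installed?

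*Combined protocol and SAP*

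**What the plan says.** D.7.a will judge feasibility by eligibility and enrollment rates and by "rates of attrition, adherence to nurse calls or video visits, and interview completion". It does not say which contacts count as adherent in Arm 2 or what the denominator is. It refers to an Appendix for the tasks and methods of each evaluation stage; that Appendix is not in the available text.

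Two fallback rules apply to Arm 2. Under D.5.a, if the application cannot be installed "within this 2-week time frame (for any reason), the intervention will continue using telephone calls only". Under D.5, for single visits, "Any scheduled video visits not able to be completed due to a technology problem will be conducted over the telephone".

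Several provisions bear on what will be known:

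- D.5.a requires a test call with telehealth staff "before scheduling their first study nurse call".
- D.5 states: "The nature and type of any technology limitations will be closely tracked".
- D.4.b states: "Following each telephone or video visit, the study nurse will enter a note in CPRS documenting the information reviewed and referrals made". It also logs nurse time on calls, including those attempted or left incomplete.
- D.4.a sets the number of contacts: "in this feasibility pilot we will limit the intervention to a total of 4 scheduled calls". D.5 gives Arm 2 as many contacts as Arm 1, at the same times.

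D.8 names the feasibility of care management by video in this population as a question that the pilot addresses.

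**The concern.** Installation is the first step at which video can fail. A Veteran who fails there stays in the program, so need not count as attrition, and can still complete the interview. Eligibility and enrollment are settled before randomization. Of the rates in D.7.a, only adherence could show the failure, and whether it does depends on a definition that the section does not give.

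The worry is a report in which attrition, adherence and interview completion all look excellent while part of Arm 2 never had a video visit. A reader planning the larger trial could then take the program's uptake as evidence that video delivery works.

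**Working it through.** The plan states no target rate, power or interval width for feasibility, so there is no figure to reproduce. The check is how far adherence can move with its definition.

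**Inputs from the protocol.** 40 dyads and 1:1 allocation (D.1); 4 scheduled calls (D.4.a).

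- Arm 2 Veterans: 40/2 = 20 (nominal; stratified randomization may shift this slightly).
- Scheduled Arm 2 contacts: 20 × 4 = 80.

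**Assumptions.** Every contact offered is taken, no single video visit fails, and k Veterans are moved to telephone under D.5.a. The documents give no value for k, so the values below are hypothetical.

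**Formulas.**

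- A, any contact over all Arm 2 contacts: 80/80.
- B, video over contacts still scheduled as video: 4(20 − k) / 4(20 − k).
- C, video over all Arm 2 contacts: 4(20 − k)/80 = (20 − k)/20.

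| k | A | B | C | Exact 95% interval for (20 − k)/20 Veterans |
|---|---|---|---|---|
| 2 | 100% | 100% | 72/80 = 90% | 68.3% to 98.8% |
| 5 | 100% | 100% | 60/80 = 75% | 50.9% to 91.3% |
| 8 | 100% | 100% | 48/80 = 60% | 36.1% to 80.9% |

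Each Veteran moved costs 4/80 = 5 points on C and nothing on A or B. The arithmetic behind the concern is therefore right.

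**How open is the choice?** D.7.a speaks of rates in the plural and names nurse calls and video visits separately, which suggests calls for Arm 1 and video for Arm 2. It does not commit to one pooled figure. Reading B treats a moved Veteran as having nothing scheduled, which fits poorly with D.5, where each Arm 2 Veteran has the same four contacts as in Arm 1. Reading A is a sensible measure of program uptake and the natural one for comparing arms. Reading C is the measure of video delivery. An analyst can report both A and C.

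**Will the counts exist?** Moving a Veteran changes how every later contact is arranged. Video visits are scheduled through the facility telehealth team, and a test call comes before the first nurse contact (D.5.a). Staff must therefore know, Veteran by Veteran, who is on video. This is an inference from the procedures, since the protocol does not list delivery mode among the contents of the contact note. The tracking in D.5, the notes and call log in D.4.b, the technology questions in the interviews (D.6.b) and the System Usability Scale with its technical support item (D.7.b) add further sources.

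**How large could k be?** One might borrow from Table 1 in B.7.c, where 75% of 40 surveyed Veterans had used the internet in the last year: 1 − 0.75 = 0.25, and 0.25 × 20 = 5. That is no forecast. This study requires an email address (D.2.a), lends an iPad to those without one, may pre-install the application and offers IT support (D.5.a), and expects the Care Partner to help with the technology (D.2.e).

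**The case for a change.** The best case for a change is that tracking a problem is different from promising to report it. The tracking sentence in D.5 follows the rule on single failed visits and speaks of technology, whereas D.5.a covers non-installation for whatever reason. A Veteran who simply never got round to installing might fall outside that tracking. B.4.a cites an earlier study's share of video visits completed as scheduled (93%) as evidence of feasibility, and this pilot has no clear counterpart until someone decides whether moved Veterans stay in the denominator. A count and a small table would cost almost nothing.

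Most of this stands as description. D.7.a leaves adherence undefined, the available text lists no installation rate, and a non-technology reason for failure is the least well covered case. The argument does not show that the plan leads to a wrong result. It needs an analyst to choose an unhelpful denominator, to leave out the number moved although D.8 asks about video, and to disregard the records and interviews. It also assumes that the Appendix is silent, which cannot be checked. The gain from writing the rule down is clarity only.

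**Conclusion.** No change follows. D.7.a leaves a descriptive denominator unstated, and the effect of the choice is 5 points on the video-delivery rate for each Veteran moved, with none on any-mode adherence. How many will be moved is unknown, and D.5.a contains several measures to keep the number low. The study does no statistical testing (D.7.b), and no feasibility threshold in the available text would be crossed by moving from one reading to another.

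The conclusion rests on two assumptions: that staff will know which Veterans were moved, which the scheduling procedure makes hard to avoid, and that a report on video feasibility will say how many there were. An author who wants to be explicit can give the number and percentage of all Veterans randomized to Arm 2 who were moved, with reasons, and split the scheduled Arm 2 contacts into video, telephone fallback and missed. That is a reporting option, and the plan does not have to be amended to allow it.
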